6.3.6. Analysis of immunogenicity by Frailty status

The analysis of immunogenicity will be categorised by vaccination group and frailty status. The primary analysis will be based on the ATP cohort for analysis of immunogenicity.

6.3.6.1. Humoral immune response

Humoral immune response will be assessed and analysed in the ATP cohort for analysis of immunogenicity – Humoral.

Descriptive statistics

For the humoral immune response, at each timepoint that a blood sample is available (Months 0, 3, 14, 26 and 38), the following parameters (with 95% CIs) will be tabulated by vaccination group and frailty status:

- Geometric mean concentrations (GMCs) of anti-(gE/VZV) Ab with 95% confidence interval (CIs);
- Humoral seropositivity rates with exact 95% CIs;
- Vaccine response rates with 95% CIs;

Inferential Analyses

No inferential analysis will be carried out on the humoral immune response data.

204878 (ZOSTER-064) Statistical Analysis Plan Amendment 1

6.3.6.2. Cell-mediated immune response

Cell-mediated immune response will be assessed and analysed in the ATP cohort for analysis of immunogenicity – CMI.

The CMI analyses was performed for ZOSTER-006 only in the Immunogenicity subset in three countries (Czech Republic, Japan and United States) at designated sites that had access to a PBMC processing facility within the acceptable time window from sample collection to PBMC processing. The CMI subset contained approximately 350 subjects. We are expecting some attrition of data, i.e. some centres who took part in the ZOSTER-006 may not take part in the ZOSTER-064. In addition, we are expecting that approximately 5% of subjects will be classified as frail. As a consequence, the analysis of CMI by frailty status will only be carried out if we have a minimum of 20 CMI subjects classified as frail.

Descriptive statistics

For CMI response, the following parameters (for gE and VZV specific CD4[2+] frequency and CD4[+2] T-cell following induction with gE and VZV) will be tabulated by vaccination group, overall and by frailty status at Months 0, 3, 14, 26 and 38:

- descriptive statistics of the frequency of CD4 T-cell secreting at least two different cytokines (IFN-γ, IL-2, TNF-α, CD40L) to both VZV and gE antigens;
- descriptive statistics of the frequency of CD4 T-cell secreting at least IFN-γ and another cytokine (IL-2, TNF-α, CD40L) to both VZV and gE antigens;
- descriptive statistics of the frequency of CD4 T-cell secreting at least IL-2 and another cytokine (IFN-γ, TNF-α, CD40L) to both VZV and gE antigens;
- descriptive statistics of the frequency of CD4 T-cell secreting at least TNF-α and another cytokine (IFN-γ, IL-2, CD40L) to both VZV and gE antigens;
- descriptive statistics of the frequency of CD4 T-cell secreting at least CD40L and another cytokine (IFN-γ, IL-2, TNF-α) to both VZV and gE antigens;
- Vaccine response rate with exact 95% CI at Months 3, 14, 26 and 38 (only in the gE-specific CD4[2+] T-cell frequency at Months 3, 14, 26 and 38)

Inferential Analyses

No inferential analysis will be carried out on the CMI data.

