The goal was to include all evaluable subjects in the statistical analysis at a specific timepoint, i.e., by including all the subjects not impacted by the elimination code for a specific Adapted ATP cohort for immunogenicity. For the criterion impacted only a specified timepoint (specified blood sampling interval), the subject was excluded from the analysis at that timepoint. For the criteria impacting a specified timepoint and the subsequent ones (e.g., medication forbidden by the protocol), the subject was excluded from the analyses performed at that timepoint onwards. For the criteria impacting all timepoints (e.g., not received two doses), the subject was excluded from the analyses at all-timepoints.

For the analysis of humoral immunogenicity, ATP cohort was further defined as ATP cohort for immunogenicity – Humoral.

For CMI the analysis will be performed on all the samples available (TVC) due to low number of samples.

Compared to the criteria applicable for the ATP cohort for analysis of safety, additional criteria for the ATP cohort for immunogenicity were the following:

- Administration of any medication forbidden by the protocol
- Underlying medical condition forbidden by the protocol
- Concomitant infection related to the disease under study (VZV) which might have influenced immune response
- Concomitant infection not related to the disease under study (VZV) which might have influenced immune response
- Vaccination done but not compliant with Dose 1- Dose 2 vaccination schedules (dates of vaccination not corresponding to protocol intervals or unknown vaccination dates)
- Blood sample taken but not compliant with blood sampling schedules (dates of BS not corresponding to adapted protocol intervals or unknown BS/vaccination dates)
- Serological results not available for antigens POST vaccination (including lost samples, not done, unable to test, absence of parallelism)
- Subject did not belong to the specified Immunogenicity subset
- The subject did not receive two doses

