10.7.7. Analysis of immunogenicity

The analysis will be based on the immunogenicity data from the ZOSTER-064 population for subjects in the adapted ATP for analysis of humoral immunogenicity, and for subjects in the TVC for analysis of CMI, respectively (Section 10.5.3).

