10.9. Conduct of analyses

Any deviation(s) or change(s) from the original statistical plan outlined in this protocol will be described and justified in the final study report.

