5. STUDY POPULATION

5.1. Total Vaccinated cohort

The TVC will include all subjects in the TVC in ZOSTER-006 or ZOSTER-022 who were enrolled at centres participating in ZOSTER-064. All subjects in the TVC in ZOSTER-006 or ZOSTER-022 who were enrolled at centres not participating in ZOSTER-064 will be excluded from the TVC.

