5.4. According-To-Protocol cohort for analysis of immunogenicity

The ATP cohort for analysis of immunogenicity will consist of all subjects in the ATP cohort for analysis of immunogenicity in ZOSTER-006 or ZOSTER-022 who were enrolled at centres participating in ZOSTER-064.

For the immunogenicity tables where different timepoints are presented, the concept of "Adapted ATP cohort for immunogenicity" will be used to denote that for each timepoint, the corresponding ATP cohort for immunogenicity will be used.

More specifically,

- The analyses at the timepoints Month 0 and Month 3 will be based on the ATP cohort for immunogenicity Month 3;
- The analysis at the timepoint Month 14 will be based on the ATP cohort for immunogenicity Month 14;
- The analysis at the timepoint Month 26 will be based on the ATP cohort for immunogenicity Month 26;
- The analysis at the timepoint Month 38 will be based on the ATP cohort for immunogenicity Month 38;

For the analysis of humoral immunogenicity, ATP cohort is further defined as ATP cohort for immunogenicity – Humoral.

Similarly, for the analysis of cell mediated immunogenicity, ATP cohort is further defined as ATP cohort for immunogenicity – CMI.

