9. CHANGES FROM PLANNED ANALYSES

- In the protocol the following secondary objective was intended for baseline only:
 - To present the distribution of SF-36 and EQ-5D scores in subjects included in ZOSTER-006 and ZOSTER-022 at baseline by country to allow comparison with normative values for those questionnaires in the general population of the countries participating in the study.
 - In order to align with the corresponding endpoint, the analysis will be performed at baseline, Months 14, 26 and 38 by country and gender
- The definition of the TVC, mTVC and ATP cohorts have been clarified. In order to minimize bias it was decided that only subjects belonging to centres that participate in ZOSTER-064 will be included. Subjects with data already encoded as part of the ZOSTER-006 or ZOSTER-022 studies will be excluded if the centre to which they belong did not take part in the ZOSTER-064.
- SAEs and pIMDs will not be described in detail as no new safety data was collected in ZOSTER-064 and all SAEs and pIMDs were described in detail in the ZOSTER-006 and ZOSTER-022 CSRs
- Due to the large number of QoL tables generated as a result of the planned analysis by various categories, the key summary tables will be presented as post-text tables in the CSR and more detailed tables will be presented separately in an Annex

204878 (ZOSTER-064) Statistical Analysis Plan Amendment 1

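### The SAP analyses cell-mediated immunity in the ATP cohort where the protocol specifies all available samples (TVC), and it does not declare the change

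*SAP*

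**What the plan says.** **SAP (Amendment 1).** Section 5.4 sets up a CMI version of the ATP immunogenicity cohort: "for the analysis of cell mediated immunogenicity, ATP cohort is further defined as ATP cohort for immunogenicity" (CMI). Section 6.3.6 covers immunogenicity as a whole: "The primary analysis will be based on the ATP cohort for analysis of immunogenicity". Section 6.3.6.2 applies this to CMI: "Cell-mediated immune response will be assessed and analysed in the ATP cohort for analysis of immunogenicity" (CMI). No CMI analysis on the TVC is described anywhere in the current SAP.

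**Protocol.** Section 10.5.3 takes ATP as the general immunogenicity cohort and then makes an exception: "For CMI the analysis will be performed on all the samples available (TVC) due to low number of samples". Section 10.7.7 repeats the split, with adapted ATP for humoral data and, for the other part, "for subjects in the TVC for analysis of CMI, respectively".

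**Declared changes.** SAP section 9 lists four changes. The one on cohorts says that the TVC, mTVC and ATP definitions were clarified, and gives this content: "In order to minimize bias it was decided that only subjects belonging to centres that participate in ZOSTER-064 will be included". It does not mention moving CMI from the TVC to ATP. Protocol 10.9 states: "Any deviation(s) or change(s) from the original statistical plan outlined in this protocol will be described and justified in the final study report".

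**The frail minimum.** SAP 6.3.6.2 also makes the by-frailty CMI analysis conditional on at least 20 CMI subjects classified as frail. It cites a subset of about 350, an expected frail share of about 5%, and some attrition of unstated size from non-participating centres.

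**The concern.** The protocol states its CMI rule twice and gives a reason: there are too few samples to discard any. The SAP reverses the rule without saying so. Someone checking section 9 would conclude that the CMI cohort still follows the protocol. The SAP's document history ties Amendment 1 to protocol Administrative Change 3, the current version, so the mismatch is not a matter of the SAP lagging behind the protocol. The superseded SAP of November 2018 already placed CMI in the ATP cohort, and its list of changes was silent on this too.

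At stake is the study's only tertiary objective, the description of CMI by frailty status. The ATP rule in SAP 6.3.6.2 governs all CMI tabulation, so the tables by vaccination group and overall lose samples as well as the by-frailty tables.

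**Working it through.** The main point is a comparison of texts. The documents derive no sample size for CMI, so there is no planned figure to reproduce.

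**1. Cohort rules side by side**

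| Data | Protocol 10.5.3 and 10.7.7 | SAP 5.4, 6.3.6 and 6.3.6.2 |
|---|---|---|
| Humoral | Adapted ATP | ATP (humoral) |
| CMI | All available samples, TVC | ATP (CMI) |

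The documents agree on humoral data and disagree on CMI.

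**2. Direction of the effect.** Protocol 10.5.3 lists the criteria that ATP adds. They include forbidden medication, a forbidden underlying condition, a concomitant infection that might affect the response, non-compliant vaccination or sampling dates, and not having received two doses. By the same section, some remove a single timepoint, some remove that timepoint and all later ones, and some remove every timepoint. Each is a further restriction, so the SAP rule can only lower the number of CMI samples and cannot raise it.

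**3. Size of the effect.** The CMI subset is about 350 (protocol 10.4.1, SAP 6.3.6.2). Neither document gives the number in the ATP-CMI cohort, so the loss cannot be calculated. For scale only, assumed losses of 10% and 20% would be 350 × 0.10 = 35 and 350 × 0.20 = 70 subjects.

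**4. Whether section 9 covers it.** Its cohort entry restricts the cohorts to participating centres, in line with SAP 5.1, under which subjects "who were enrolled at centres not participating in ZOSTER-064 will be excluded from the TVC". Centre participation and the ATP criteria are separate restrictions. Declaring the first does not declare the second.

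**5. Side check on the minimum of 20 frail subjects**

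- Expected frail = n × p. With n = 350 and p = 0.05, this is 17.5, below 20 before any attrition.
- P(X ≥ 20) = 1 − Σ C(n,k) pᵏ (1−p)ⁿ⁻ᵏ, summed over k = 0 to 19:

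| n (assumed loss) | p = 0.05 (SAP) | p = 0.06 (assumed) |
|---|---|---|
| 350 (none) | 0.302 | 0.621 |
| 315 (10%) | 0.165 | 0.430 |
| 280 (20%) | 0.071 | 0.242 |

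The SAP gives no attrition figure. Both loss rates are assumptions, and the 6% column tests how much depends on the SAP's approximate 5%. As section 6.3.6.2 is worded, missing the minimum withholds the by-frailty CMI tables for non-frail and pre-frail subjects as well as for frail subjects.

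**The case against.** The best defence is that ATP is a legitimate cohort for descriptive immunogenicity. It is the protocol's general rule and matches the humoral analysis. No inference is planned on CMI, and protocol 10.4.1 already expects the by-frailty results to be limited. Protocol 10.9 asks for changes to be justified in the final study report, not in the SAP, so silence in section 9 does not breach that rule and a later declaration remains possible. The number of samples lost is unknown and could be small.

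All of this stands as a limit on weight. A reader might infer that an ATP analysis of CMI is invalid, but the documents do not support that. The defect is a contradiction of a specific, reasoned protocol rule that the SAP's own list of changes omits. The general ATP rule does not settle the matter, because the protocol expressly takes CMI out of it.

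A reader might also infer that ATP exclusions fall more heavily on frail subjects and so bias the comparison. Exclusions for medication or underlying condition make that conceivable, but nothing in the documents shows it.

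On the minimum of 20, the defence is largely right. Protocol 10.7.7.2 makes these tables conditional on the data, and a prespecified number is a reasonable way to apply that. Treating the minimum as an error would go too far.

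**Conclusion.** The conflict is real: the current SAP puts all CMI data in the ATP cohort, the current protocol puts them in the TVC, and SAP section 9 does not declare the difference. The SAP should be changed or the departure declared. The effect is a loss of samples of unknown number from every CMI table, in a subset of about 350. No primary or secondary result is touched, and no error rate is involved.

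Two further inferences are not supported. First, restoring the TVC would not by itself secure the by-frailty tables: with all 350 subjects kept and 5% frail, the chance of reaching 20 is only 0.30. Second, it cannot be said that the non-frail and pre-frail categories would each be well filled, because the documents do not give their separate sizes.

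The wording of the minimum is therefore an optional improvement. At the SAP's 5% the minimum is more likely missed than met, but at 6% with no attrition the chance of meeting it is 0.62. The calculation treats 350 as the starting number and applies the SAP's general 5% to the CMI subset.

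**What to change.** In SAP 5.4, 6.3.6 and 6.3.6.2, state that CMI is analysed on all available CMI samples from subjects in the TVC as defined in SAP 5.1, that is, participating centres only. The TVC of protocol 10.5.1 should not be used for this: it also admits subjects with suspected HZ from non-participating centres, whom SAP sections 5.1 and 9 deliberately exclude.

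If the sponsor prefers ATP for CMI, add an entry to SAP section 9 that names the change and gives the reason, and repeat it in the final report as protocol 10.9 requires.

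Optionally, apply the minimum of 20 to the frail column only, count it in the same cohort as the CMI analysis, and tabulate non-frail and pre-frail subjects by vaccination group whether or not it is met.

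The cost is SAP wording, with no new data. The small downside of using the TVC is that some samples with protocol deviations enter the tables.

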7. STATISTICAL CALCULATIONS

7.1. Derived and transformed data

7.1.1. Demography

Age at vaccination

Age will be calculated as the number of years between the date of birth and the date of first vaccination.

To ensure that the collection of date of birth will not jeopardise the privacy of Personally Identifiable Information (PII), only a partial date of birth (MMYYYY) was collected.

Therefore, the 15th of the month will be used to replace the missing date.

In case the month is missing, the date will be replaced by the June 30th of the year.

Note that due to incomplete date, the derived age may be incorrect by 1 month when month is missing from the birthdate. This may lead to apparent inconsistency between the derived age and the eligibility criteria/the age group used for randomization.

7.1.2. Efficacy data

Details of derived and transformed efficacy data including the methodology behind the VE is contained in the SAPs for the ZOSTER-006 and ZOSTER-022 studies.

7.1.3. Safety

Details of derived and transformed safety data is contained in the SAPs for the ZOSTER-006 and ZOSTER-022 studies.

7.1.4. Immunogenicity

7.1.4.1. Humoral immune response

Full details of the methods used in the humoral immune response analyses are contained in the ZOSTER-006 and ZOSTER-022 SAPs (Demog, Safety, Immuno).

7.1.4.2. Cellular-mediated immune (CMI) response

Full details of the methods used in the CMI analysis including calculation of the frequency of antigen-specific (gE or VZV) CD4[2+] T-cells for each individual subject and the definition of CMI vaccine response to gE and VZV are contained in the ZOSTER-006 SAP (Demog, Safety, Immuno).

7.2. Quality of Life data

7.2.1. SF-36 and EQ-5D

Details of the derivation of the 8 scales generated from the SF-36 and the derivation of the utility score from the EQ-5D are contained in the QoL SAPs for the ZOSTER-006 and ZOSTER-022 studies.

7.2.2. HZ Burden of illness

The HZ BOI scores are based on the ZBPI questionnaire already encoded in the ZOSTER-006 and ZOSTER-022 studies.

Full details of the ZBPI questionnaire and the methodology behind the calculation of the HZ BOI scores are contained in the QoL SAPs for the ZOSTER-006 and ZOSTER-022 studies.

7.3. Frailty Index

Frailty status will be measured in relation to the accumulation of deficits using a frailty index (FI) adapted from the model proposed by Mitnitski et al. [Mitnitski, 2001]. The different aspects of frailty composing the frailty index will be assessed through the medical history and components of the *SF-36* and *EQ-5D* questionnaires recorded prevaccination Dose 1.

The total frailty score will be between 0 and 41. The subject's pre-vaccination questionnaires will contribute a max score of 29 and the medical history will contribute a max score of 12. Table 3 details the components of the SF-36 and EQ-5D questionnaires that contribute to the calculation of the frailty index.

204878 (ZOSTER-064) Statistical Analysis Plan Amendment 1

Table 3 Detail of SF-36 and EQ-5D components of frailty Index

Item	Scoring method based on response to question	Max Contribution to Frailty Index
SF-36 Q1	Poor=1,	1
5/ 00 Q1	Fair=0.5	'
	Good=0,	
	Very good=0	
	Excellent=0	
SF-36 Q11A-11D	Q11A, Q11C	4
S. 33 Q. D. 1.2	Definitely true=1	·
	Mostly true=0.5	
	Don't know=0	
	Mostly false=0	
	Definitely false=0	
	Q11B, Q11D	
	Definitely true=0	
	Mostly true=0	
	Don't know=0	
	Mostly false=0.5	
	Definitely false=1	
SF-36 Q3I - Q3J	Limited a lot=1	10
	Limited a little=0.5	
	Not limited at all=0	
SF-36 Q9A - Q9I	Q9A, Q9D, Q9E, Q9H :	9
	All of the Time=0	
	Most of the time=0	
	Some of the time=0	
	A little of the time=0.5	
	None of the time=1	
	Q9B, Q9C, Q9F, Q9G, Q9I:	
	All of the Time=1	
	Most of the time=0.5	
	Some of the time=0	
	A little of the time=0	
	None of the time=0	
SF-36 Q2 Compared to one week before,	Much worse=1,	1
how did the subject rate his / her health	Somewhat worse=0.5,	
in general?	Same=0	
	Somewhat better=0	
	Better=0	
EQ-5D Mobility	No Problems=0	1
	Some Problems=0.5	
	Confined to bed=1	
EQ-5D Anxiety	No Anxiety=0	1
	Moderate Anxiety=0.5	
	Extreme Anxiety=1	
EQ-5D Self care	No Problems=0	1
	Some Problems=0.5	
	Inability to wash or dress himself	
	/herself=1	
EQ-5D Usual activities	No Problems=0	1
	Some Problems=0.5	
	Inability to perform usual activities=1	
Total		29

204878 (ZOSTER-064) Statistical Analysis Plan Amendment 1

The medical history is divided into 12 selected categories; each category contributing a score of 0 or 1. The coded combined ZOSTER-006 and ZOSTER-022 medical history database will be searched and events that fall into any one of the 12 categories will be selected Table 4 details the MedDRA terms that will be used to search the database. If a subject had any one of the listed events in a category they would be assigned a max score of 1 for that category and a max score of 12 overall.

The frailty index is then calculated by combining the accumulation of deficits into a score from 0 to 1: frailty index = (accumulation of deficits) / (41 – nmissQoL) where nmissQoL is the number of missing components of the 29 items from the SF-36 and EQ-5D questionnaires. If a subject has more than 10 missing QoL components the frailty index will not be calculated.

Each subject will then be assigned to one of three categories, Non-Frail, Pre-Frail and Frail based on the frailty index.

• If the frailty index is **less than or equal to** 0.08 then the subject is classified as Non-Frail. If the score is greater than 0.08 **but less than or equal to** 0.25 then the subject is classified as pre-frail. If the score is **greater than** 0.25 then the subject is classified as Frail. Subjects without a frailty index score will be classified as missing.

Table 4 Detail of Medical history search items

2 (W IDDA ' 400 I T
Category	MedDRA version 18 Search Terms
Cancer	Malignancy related conditions (SMQ)
	Malignant tumours (SMQ)
Diabetes Mellitus	Diabetes mellitus (incl subtypes) (HLT)
	Diabetic complications (HLGT)
High Blood Pressure,	Hypertension (SMQ)
Heart Attack	Ischaemic heart disease (SMQ)
CHF	Cardiac failure (SMQ)
Cerebrovascular	Central nervous system vascular disorders (SMQ)
Disease	
Arthritis	Arthritis (SMQ)
Chronic Lung Disease	Asthma/bronchospasm (SMQ)
•	Interstitial lung disease (SMQ)
	Pulmonary hypertension (SMQ)
	Chronic Obstructive Pulmonary Disease (PT) / Infective exacerbation of chronic
	obstructive airways disease (PT)
	Bronchiectasis (PT) /Infective exacerbation of bronchiectasis (PT)
	Cystic fibrosis (PT)/ Cysitic fibrosis lung (PT) / Infective pulmonary exacerbation of
	cystic fibrosis (PT)
	Chronic respiratory disease (PT)
	Chronic respiratory failure (PT)
Stomach or Intestinal	Gastrointestinal ulceration (SMQ)
Ulcers	,
Migraine	Migraine headaches (HLT)
· ·	Migraine prophylaxis (PT)
Cataract	Cataract Conditions (HLT)
	Cataract operation (PT)
	Cataract diabetic (PT)
	Cataract operation complication (PT)
Glaucoma	Glaucoma (SMQ)
0140 01 1 1 1	MadDDA quarias ULCT: High Lavel Crown Torm ULT: High Lavel Torm DT: Draferred Torm

• SMQ: Standardised MedDRA queries. HLGT: High Level Group Term. HLT: High Level Term. PT: Preferred Term

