6.3.1. Exclusion criteria for data encoding

- Subjects who developed a suspected HZ case during ZOSTER-006 and ZOSTER-022 (since their QoL questionnaires were encoded in the eCRF for ZOSTER-006 and ZOSTER-022).

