8.3.4. Study conclusion

The investigator/delegate will:

- review all the data encoded in eCRF to ensure accuracy and completeness,
- sign the eCRF.

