10.4. Determination of sample size

Approximately 30,000 subjects were enrolled in ZOSTER-006 and ZOSTER-022. Out of these, approximately 1000 subjects will have developed suspected HZ cases over the course of the studies and their QoL questionnaires were encoded in the eCRF for ZOSTER-006 and ZOSTER-022, according to the protocols of those studies, respectively. Therefore approximately 29,000 subjects whose QoL questionnaires were completed and collected but not encoded in the earlier studies, will be encoded in the ZOSTER-064 study. Data encoded as part of the 064 study will be combined with data from the ZOSTER-006 and ZOSTER-022 studies to ensure that subjects data are available for analysis, as appropriate taking into account inclusion/exclusion criteria (see section 6) and cohorts for analysis (see section 10.5).

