		11 FEB 2019

2. STUDY DESIGN

This is a retrospective, observational study, in which pooled data from the ZOSTER-006 and ZOSTER-022 will be analysed. As a consequence no new subjects will be enrolled in this study and no new ICF will be required from study subjects.

In ZOSTER-006 and ZOSTER-022, encoding of Quality of Life (QoL) questionnaires (*SF-36*, *EQ-5D*) was only performed for subjects who developed a suspected Herpes Zoster (HZ) episode during the study. This was done to assess the QoL of subjects who developed suspected cases of HZ between the vaccine group and the placebo group. The remaining study subjects who did not develop suspected cases of HZ completed the questionnaires; however, these questionnaires were never encoded or analysed as part of ZOSTER-006 and ZOSTER-022. The remaining questionnaires will be encoded in ZOSTER-064. These questionnaires will be used, in association with already encoded medical history from each subject, to derive a frailty index and thus assign each subject to a baseline frailty status (non-frail, pre-frail, frail, missing). This will allow efficacy, safety and immunogenicity data to be re-analysed according to frailty status.

The following group names will be used for the statistical analyses:

l	Group order in tables	Group label in tables	Group definition for footnote	
	P	HZ/su	Herpes Zoster subunit vaccine	
ĺ	D	Placebo	Placebo	

The following sub-groups will be used for the statistical analysis:

Table 1 Details of subgroups

Sub-group category	Sub-group order in tables	Sub-group label in tables	Sub-group definition for footnote
Frailty Status	PP -D	Non-Frail	Subjects with frailty index score ≤0.08
	D	Pre-Frail	Subjects with frailty index score >0.08 and ≤0.25
		Frail	Subjects with frailty index score >0.25
		Unknown	Subjects who were not assigned a Frailty Status
Gender	nder M		Male Subjects
		Female	Female Subjects

204878 (ZOSTER-064) Statistical Analysis Plan Amendment 1

Table 2 Details of age and region subgroups

Analysis by age group

ord	b-group Ier in Iles	Sub-group label in tables	Sub-group definition for footnote	Pooled Groups 1 label in tables	Pooled Groups 2 label in tables
PP -D		50-59YOA	50-59 years old subjects	50-59YOA	< 70YOA
	60-69YOA 70-79YOA		60-69 years old subjects	60-69YOA	< 70YOA
			70-79 years old subjects	70-79YOA	≥ 70YOA
		80-89YOA	80-89 years old subjects	≥ 80YOA	≥ 70YOA
		≥ 90YOA	≥ 90 years old subjects	≥ 80YOA	≥ 70YOA

Analysis by country/region

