5.3. Modified Total Vaccinated cohort

The mTVC will include all subjects in the mTVC in ZOSTER-006 or ZOSTER-022 who were enrolled at centres participating in ZOSTER-064.

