6.3.1.1. Analysis of Completion of SF-36 and EQ-5D

Compliance with completion of both SF-36 and EQ-5D questionnaires will be summarised by country at each time point (Months 0, 14, 26 and 38) and overall. This compliance will be presented for the TVC and will include in the calculation both newly encoded and previously encoded questionnaires.

% Completion will be defined for each time point as follows:

% Completion = $100 \times N1 / N2$

Where:

N1 = number of subjects with a completed SF-36/EQ-5D questionnaire.

N2 = number of subjects for whom a questionnaire was expected.

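### Could missing frailty indices among subjects without suspected HZ inflate HZ incidence by frailty category enough to need a change to the SAP?

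*SAP*

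**What the plan says.** Two data routes feed the frailty index. Protocol 6.3.1 leaves suspected HZ cases out of the new encoding, "since their QoL questionnaires were encoded in the eCRF for ZOSTER-006 and ZOSTER-022". For everyone else, Protocol 10.4 states that "approximately 29,000 subjects whose QoL questionnaires were completed and collected but not encoded in the earlier studies, will be encoded in the ZOSTER-064 study". Under SAP 7.3 the index is not calculated when more than 10 of the 29 questionnaire items are missing, and "Subjects without a frailty index score will be classified as missing".

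The SAP recognises that the two routes can cause bias. Section 9 says: "In order to minimize bias it was decided that only subjects belonging to centres that participate in ZOSTER-064 will be included". Within those centres nobody is removed. Section 5.3 says: "The mTVC will include all subjects in the mTVC in ZOSTER-006 or ZOSTER-022 who were enrolled at centres participating in ZOSTER-064".

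Subjects without an index have a place in the plan. SAP 2 counts missing among the frailty statuses, and Table 1 lists an Unknown subgroup, defined as "Subjects who were not assigned a Frailty Status", among the subgroups for analysis. Completion is reported by country and time point under SAP 6.3.1.1: "This compliance will be presented for the TVC and will include in the calculation both newly encoded and previously encoded questionnaires". Protocol 8.3.4 has the investigator "review all the data encoded in eCRF to ensure accuracy and completeness", and Protocol 11.2 adds source verification by monitors.

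**The concern.** Whether a baseline form is already on file depends on the outcome. A site that encodes only part of its remaining forms loses frailty status almost entirely among subjects without HZ, while its cases keep theirs. The numerator of HZ incidence by frailty category stays whole and the denominator shrinks. SAP 9 deals with this between centres by dropping those that do not take part, but the same asymmetry can occur inside a participating centre, where the mTVC keeps all its subjects.

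The affected figure matters. HZ incidence in the mTVC is a secondary endpoint, SAP 7.6 lists the incidence rate among efficacy outputs, and Protocol 1.1 counts higher incidence in frail subjects as part of the benefit argument. The completion report pools the two routes. SAP 6.3.2 and 6.3.3 do not say in so many words that the Unknown row will be printed, and no sensitivity analysis for a missing index is specified.

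**Working it through.** **The plan's own figure.** 30,000 enrolled - 1,000 suspected cases = 29,000 to be newly encoded. Protocol 10.4 agrees.

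**Inputs.** From the documents: 30,000 subjects and about 1,000 suspected cases (Protocol 10.4); 10 cases per 1,000 person-years at age 60 and over (Protocol 1.1.1); about 5% frail (SAP 6.3.6.2). Assumed, because the documents do not give them: 1:1 allocation, 3.2 years of follow-up, vaccine efficacy 90%, and the encoding fractions.

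- Placebo confirmed cases: 15,000 x 3.2 x 10/1,000 = 480. Vaccine: 10% of that, 48.
- Suspected but unconfirmed: (1,000 - 528)/2, taken as 235 per arm.
- Other subjects: 15,000 - 480 - 235 = 14,285 placebo; 15,000 - 48 - 235 = 14,717 vaccine.
- Confirmed cases contribute on average half the follow-up, 1.6 years.

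**Formula.** Let c be the share of suspected cases with a usable index and f the share of other subjects.

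Rate = c x cases / [c x (case PY + unconfirmed PY) + f x other PY]

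Placebo with everything encoded: 480 / (768 + 752 + 45,712) = 480/47,232 = 10.16 per 1,000 PY.

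| c | f | Placebo rate | Change |
|---|---|---|---|
| 100% | 98% | 10.36 | +2.0% |
| 100% | 95% | 10.68 | +5.1% |
| 100% | 90% | 11.25 | +10.7% |
| 100% | 80% | 12.60 | +24.0% |
| 95% | 95% | 10.16 | 0 |
| 95% | 90% | 10.71 | +5.4% |
| 90% | 95% | 9.64 | -5.1% |

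The sign depends on which group is less complete. A form on file with more than 10 missing items also gives no index, so c need not be 100%.

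**Vaccine efficacy.** With everything encoded the vaccine rate is 48 / (76.8 + 752 + 47,094.4) = 1.002, so efficacy is 1 - 1.002/10.16 = 90.1%. At f = 80% in both arms it is 1 - 1.247/12.60 = 90.1%. With f = 95% in placebo and 90% in vaccine it is 1 - 1.111/10.68 = 89.6%.

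**Frail against other subjects, uniform f.** With c = 100% the inflation is 1/[s + f(1 - s)], where s is the share of follow-up held by suspected cases: 1,520/47,232 = 3.2% overall. Assume a true ratio of 2.15 and let s scale with it, to 6.9% in frail subjects. At f = 80% the inflation factors are 1.229 (frail) and 1.240 (others), so the ratio becomes 2.15 x 1.229/1.240 = 2.13. At f = 95% and 90% it is 2.15 and 2.14.

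**Against sampling error.** The exact 95% interval of a placebo rate runs from -9% to +9% with 480 cases and from -36% to +49% with 24 cases (5% of 480). The bias reaches the size of sampling error only with all categories pooled and f at about 90% or lower.

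**Would the planned outputs show it?** Suspected cases are 3.3% of subjects, so pooled completion is (1,000c + 29,000f)/30,000. With c = 100% it reads 95.2%, 90.3% and 80.7% at f = 95%, 90% and 80%. Because c cannot exceed 100%, pooled completion P gives f of at least (30,000P - 1,000)/29,000, and hence a ceiling on the inflation. The bound is approximate, since 6.3.1.1 counts completed forms and not usable indices. The Unknown row is more direct: at c = 100% and f = 95% it would hold 5% x 14,285 = 714 placebo subjects with no confirmed cases, against 714 x 3.2 x 10.16/1,000 = 23 expected.

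**The case for a change.** The strongest argument for a change is that the sponsor accepted the principle in SAP 9 and then applied it only between centres. The superseded SAP of November 2018 planned separate completion figures for newly encoded forms and removed centres encoding under 50% from the predictor analysis, so incomplete encoding was foreseen. The remedy would need only wording and programming. If encoding also depended on frailty, the damage would be worse than a common scaling: with 80% of frail and 95% of non-frail subjects without suspected HZ encoded, equal true incidence would show a false frail-to-non-frail ratio of 1.18.

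Part of this stands. The current text does not split completeness by case status, and it leaves the row layout of the efficacy and burden-of-illness tables to the TFL annex, which was not supplied. The rest is weaker. A difference from superseded text is not an error. Nothing in the documents reports frailty-dependent encoding. Inverse-probability weighting, the obvious sensitivity analysis, removes the common scaling, which hardly affects the frailty contrasts, but handles the harmful case poorly: in simulation with 75% of frail and 90% of other non-cases encoded, the false excess in the Frail rate fell only from +32% to +17%.

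**Conclusion.** No change to the plan is needed. The asymmetry between the two data routes is real and the arithmetic holds, but the bias requires an encoding shortfall that no document shows and that the plan sets out to avoid through full encoding, investigator review and source verification. If one occurred, absolute placebo incidence would rise by roughly c/f: 2% to 11% for f between 98% and 90% with c = 100%. Vaccine efficacy would stay at about 90.1% unless encoding differed by arm, and frail-versus-other contrasts would barely move unless encoding depended on frailty.

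Analysts working from SAP 2 would naturally carry the Unknown subgroup into the efficacy tables, and pooled completion is close enough to f to warn of trouble. SAP 6.1 and 6.2.1 also tabulate frailty status by vaccine group and by country. Protocol 10.7 and 10.8 call the work exploratory and descriptive, so reporting usable-index completeness by suspected-case status is a matter of taste. The figures rest on the assumed follow-up, allocation, efficacy and encoding fractions; with 3 or 4 years and 5 to 12 cases per 1,000 PY, the inflation at f = 80% stays between 23.8% and 24.3%. Mean burden of illness would follow the same pattern only if averaged over all subjects, which depends on parent SAPs that were not supplied.
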